6.12.2 Laboratory Data

Descriptive statistics of the observed values and change from baseline (continuous data) will be presented by treatment group and visit for each hematology, urinalysis, and serum chemistry parameters. Each measurement (continuous data) will be classed as below, within, or above normal range, based on ranges supplied by the laboratory used. Shift tables in relation to the normal range from baseline to each post-baseline visit will be presented. For categorical laboratory parameters, subject counts within each category will be summarized. Shift tables from baseline to each post-baseline visit will also be presented, as applicable.

A listing of out of normal range laboratory values that are marked by investigator as clinically significant throughout the study will be presented. All laboratory assessments, including urine and serum pregnancy tests, will also be listed.

WORLDWIDE CLINICAL TRIALS
SCIENTIFICALLY MINDED • MEDICALLY DRIVEN

Revance Therapeutics, Inc.
1820201
Statistical Analysis Plan
Version 1.0
Issue Date 04-SEP-2020

6.12.3 Vital Signs

Descriptive statistics for observed values and changes from baseline in the following vital signs will be tabulated at each post-baseline visits:

- Systolic blood pressure (mmHg)
- Diastolic blood pressure (mmHg)
- Pulse rate (bpm)
- Respiration rate (breaths/min)
- Body temperature (degrees Celsius or degrees Fahrenheit)
- Body weight (kg)

All vital signs measurements throughout the study will be listed.

6.12.4 Electrocardiogram Data

Descriptive statistics for observed values and changes from baseline in the following ECG variables will be tabulated at each post-baseline visits:

- Heart rate (bpm)
- PR interval (ms)
- RR interval (ms)
- QRS complex (ms)
- QT interval (ms)
- QTc interval (ms) [Bazett's formula - QTcB]
- QTc interval (ms) [Fridericia's formula - QTcF]

Shift tables in relation to the overall interpretation (Normal, Abnormal Not Clinically Significant [NCS], and Abnormal Clinically Significant [CS]) from baseline to each post-baseline visit will be presented.

All ECG assessments throughout the study will be listed.

6.12.5 Foot and Ankle Examination

Examination for the foot will be conducted, including ankle, toe, and subtalar range of motion, foot motor strength, location of pain, and examination of the heel fat pad and Tinel's sign. The presence of toe deformities, bunions, ulcers, and/or sores will also be recorded. The feet will also be examined for signs of swelling, pitting edema, infection, or vascular abnormalities.

Descriptive statistics of the observed values will be presented for each quantitative parameter by treatment group and study visit. Subject counts within each category will be summarized by treatment group and study visit for the qualitative parameters.

All foot and ankle examination data throughout the study will be listed.

6.12.6 Physical Examination

The body systems within physical examination data at Screening will be summarized by treatment group and finding (Normal, Abnormal NCS, Abnormal CS).

All physical examination data throughout the study, including details of clinically significant findings for each body system, will be listed.

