5 PROTOCOL SUMMARY

5.1 SYNOPSIS

Title: A Phase II, Prospective, Randomized, Double-Blind, Multi-center, Placebo-Controlled Trial of DaxibotulinumtoxinA for Injection for the Management of Plantar Fasciitis

Study Description: This is a randomized, double-blind, placebo-controlled, multi-center study of two doses of daxibotulinumtoxinA (DAXI) for injection in adult subjects with unilateral plantar fasciitis (PF).

Approximately 150 subjects recruited from approximately 20 investigator sites in the US will be randomized

PIs, site staff (excluding unblinded dose preparers), subjects, and

The primary efficacy endpoint is the change from baseline in the Numeric Pain Rating Scale (NPRS) score at Week 8.

In case of no improvement, defined as no change or worsening of the NPRS score from baseline, Week 8 will serve as the early completion visit for the subject (i.e., the “early study completer”). Subjects who experience any treatment benefit (any decrease from baseline on NPRS score) will continue in the study. NPRS scores will be collected by subjects daily in an ePRO diary. Algometry, Clinical Global Impression of Change (CGIC), and Patient-reported Outcomes (PROs; i.e., Foot Function Index [FFI], Foot and Ankle Ability Measure [FAAM], Patient Global Impression of Change [PGIC] and Treatment Satisfaction Questionnaire [TSQ]) will be performed at prespecified time points during the study, as efficacy evaluations. Safety will be assessed based on adverse events (AEs), clinical laboratory parameters, vital signs, 12-lead electrocardiograms (ECGs), physical examination, and the Columbia – Suicide Severity Rating Scale (C-SSRS).

Trial Objective:

- To compare the efficacy and safety of two doses of DAXI for injection versus placebo for managing plantar fasciitis

Endpoints:

Primary Efficacy Endpoint:

- Change from baseline in the NPRS score, which is recorded within 15 minutes after stepping out of bed in the morning and averaged over 5 days (defined as 4 days prior to study visit and on the study visit day), at Week 8

Safety Endpoints

- Frequency, severity and relationship to study drug of treatment-emergent adverse events during the first 8 weeks post treatment and the overall study duration
- Frequency, severity and relationship to study drug of treatment-emergent serious adverse events during the first 8 weeks post treatment and the overall study duration

Study Population:

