12.1.3 DAY 1 TREATMENT VISIT

The following procedures will be completed **pre-treatment**:

[figure not shown]
- Confirm subject eligibility.
- Medical history and physical examination
- [REDACTED]
- Collect vital signs (BP, pulse, temperature, respiration rate) and weight
- C-SSRS (since last visit)

After study eligibility is confirmed, as defined by the eligibility criteria in Sections 9.1 and 9.2, the

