12.3.1.2 ADVERSE EVENTS AND SERIOUS ADVERSE EVENTS

12.3.1.2.1 DEFINITION OF ADVERSE EVENTS (AE)

For this protocol, an AE is any untoward medical occurrence (e.g., sign, symptom, disease, syndrome, intercurrent illness, clinically significant abnormal laboratory finding, injury or accident) that emerges or worsens following administration of IP and until the end of study participation that may not necessarily have a causal relationship to the administration of the IP. An AE can therefore be any unfavorable and/or unintended sign (including a clinically significant abnormal laboratory result), symptom, or disease temporally associated with the use of an IP, whether or not considered related to the IP. A treatment-emergent AE is one that occurs after any period of exposure to treatment.

Pre-existing conditions, which increase in frequency or severity or a change in nature as a consequence of an IP use will also be considered an AE.

An unexpected AE is an adverse reaction, the nature or severity of which is not consistent with the applicable product information (e.g., Investigator's Brochure for an unapproved IP or package insert/summary of product characteristics for an approved product).

Any clinically significant change in the study safety evaluations, (e.g., vital signs, laboratory results, ECG, injection site evaluation, physical/neurological examinations, etc.) post-treatment must be reported as an AE.

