12.3.6 PHYSICAL EXAMINATIONS

Physical examination will include neurological examination; the PE will include examination of the face, general appearance, skin, neck (including thyroid), eyes, ears, nose, throat, heart, lungs, abdomen, lymph nodes, and extremities. Urogenital exam need only be completed if clinically indicated. At post-treatment visits, the physical examination may be abbreviated, as deemed medically appropriate at the discretion of the PI; the neurological examination must be conducted at a minimum. Significant physical examination findings that are present prior to IP administration are to be included on the Medical History page.

Significant physical examination findings which meet the definition of an AE will be recorded on the AE page post-treatment.

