6.2.2 Baseline

Unless otherwise specified, baseline is defined as the last non-missing value (either scheduled, unscheduled or repeat) before the subject receives the dose of study drug at Day 1. For re-screened subjects, if assessment was not done on the second screening, the initial screening result will be considered.

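### SAP 6.12.6 tabulates the physical examination by arm only at Screening; post-dose findings are listed, so non-significant neurological changes outside the foot that are not recorded as AEs reach no by-arm table

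*SAP*

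**What the plan says.** The protocol counts the physical examination among its safety assessments (Protocol 5.1: "Safety will be assessed based on adverse events (AEs), clinical laboratory parameters, vital signs, 12-lead electrocardiograms (ECGs), physical examination"). Protocol 12.3.6 makes the neurological part integral ("Physical examination will include neurological examination"). It lets the investigator shorten the examination after treatment, but with one limit: "the neurological examination must be conducted at a minimum". An examination is also done on Day 1 before the injection (Protocol 12.1.3: "Medical history and physical examination").

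SAP 6.12.6 plans two outputs. The first is a by-arm summary: "The body systems within physical examination data at Screening will be summarized by treatment group and finding (Normal, Abnormal NCS, Abnormal CS". The second is a listing: "All physical examination data throughout the study, including details of clinically significant findings for each body system, will be listed". The section plans nothing else, and no redaction is visible inside it.

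**The concern.** At Screening no drug has been given, so a by-arm table of examination findings describes the groups at entry and says nothing about the safety of the injection. The examinations that could say something are those after dosing, and for them the section plans only a listing.

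Part of the trial's objective is to compare the safety of two doses with placebo. If mild neurological signs were somewhat more frequent in the DAXI arms, each judged not clinically significant on its own, a reader of the report would have to find and count them line by line. The reader would also not know how many subjects in each arm had been examined.

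**Working it through.** No formula applies: the point concerns which outputs are planned, and the plan gives no figure to reproduce. The check is to read SAP 6.12.1 to 6.12.8 against the protocol's rules for the examination and for AE reporting.

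**1. Post-dose output for each assessment in SAP 6.12** (all by treatment actually received, per the opening of 6.12)

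| SAP section | Post-dose table planned |
|---|---|
| 6.12.1 Adverse events | Yes, TEAEs by system organ class and preferred term |
| 6.12.2 Laboratory | Yes, values, changes and shifts at each post-baseline visit |
| 6.12.3 Vital signs | Yes, values and changes |
| 6.12.4 ECG | Yes, values, changes, and a shift table in Normal / Abnormal NCS / Abnormal CS |
| 6.12.5 Foot and ankle | Yes, by arm and visit |
| 6.12.6 Physical examination | **No: Screening table, then listing only** |
| 6.12.7 Injection site | Yes, by arm and visit |
| 6.12.8 C-SSRS | Yes, post-screening, by arm |

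The physical examination is the only one of the eight without a post-dose table.

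**2. Where a post-dose examination finding can go**

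- *A clinically significant change.* Protocol 12.3.1.2.1 requires it to be reported as an AE ("Any clinically significant change in the study safety evaluations"; the physical and neurological examinations are among the examples given). Protocol 12.3.6 likewise sends significant findings that meet the AE definition to the AE page. They then appear in the by-arm TEAE tables.
- *Foot motor strength, range of motion, Tinel's sign.* These belong to the foot and ankle examination (Protocol 12.3.7) and are summarised by arm and visit under SAP 6.12.5. SAP 6.2.10 confirms that scheduled post-baseline foot and ankle data are tabulated.
- *A change from Normal to Abnormal NCS, outside the foot examination, that the investigator does not record as an AE.* Listing only.
- *The number of subjects examined, by arm and visit.* No table. AE tables do not supply it, because an AE count does not show who had the examination.

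**3. Does AE capture explain the omission?** The AE rule in Protocol 12.3.1.2.1 names vital signs, laboratory results, ECG and injection site evaluation in the same sentence as the physical and neurological examinations. The SAP still tabulates all four after dosing. So AE reporting is not treated as a substitute for a table anywhere else.

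**The case against.** The strongest case on the other side is that little is left uncovered. The AE definition is wide: it takes in any unfavourable or unintended sign, related or not, and the mild grade covers events that do not affect daily activities. Mandatory reporting of significant changes is therefore a floor, and an investigator may record lesser signs too. Weakness in the injected foot, an obvious local concern, is tabulated by arm and visit under SAP 6.12.5. The named safety endpoints are TEAEs and serious TEAEs, so the physical examination is a supporting assessment. All data are listed, SAP 6 permits extra tables in the study report, a DMC reviews safety data, and part of the AE output in SAP 6.12.1 is redacted.

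Most of this stands, and it limits the point to what is said here. It does not remove it. Whether a lesser sign becomes an AE depends on the investigator's judgement. The physical examination also covers regions far from the foot, including the face, neck, eyes, throat and lungs. A table chosen after the data are seen is weaker than one planned beforehand.

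Three stronger readings are tempting, and the documents do not support them.

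- *A reader might infer that the neurological examination is never compared between DAXI and placebo.* The AE tables and the foot and ankle tables both carry part of it.
- *A reader might infer that the Screening table breaks the SAP's own baseline rule.* SAP 6.2.2 says "baseline is defined as the last non-missing value (either scheduled, unscheduled or repeat) before the subject receives the dose of study drug", but that sentence opens with an exception for cases specified otherwise. SAP 6.12.6 names Screening outright and calculates no change from it, so there is no conflict.
- *A reader might count the lost examinations by multiplying the eight follow-up visits by about 150 subjects.* The schedule of assessments is not in the available text and the follow-up procedures in Protocol 12.1.4 are partly redacted. How many post-dose examinations each subject has is therefore unknown. The allocation is redacted too, so an illustrative split between arms would be invented.

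**Conclusion.** The point holds in a limited form. SAP 6.12.6 gives a by-arm table for the one time at which the examination cannot reflect treatment, and a listing for the rest. What is left out of every visible by-arm table is the post-dose shift from Normal to Abnormal NCS outside the foot examination, when it is not recorded as an AE, and the number examined.

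The documents give no basis for a numerical size. No test, estimate or primary conclusion changes. The planned safety outputs are descriptive, so comparison here means side-by-side tabulation and not a hypothesis test. This is a low-priority, inexpensive improvement.

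The conclusion rests on two assumptions: that the redacted parts of SAP 6.12.1 hold no table of examination findings as such, and that post-treatment findings are recorded in the same three categories as at Screening. Whether the neurological examination has its own field on the CRF is not shown, and the fix allows for either case.

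**What to change.** In SAP 6.12.6, add a descriptive shift table (Normal / Abnormal NCS / Abnormal CS) by treatment received, running from the last pre-dose examination to:

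- each post-treatment visit at which the examination is done, and
- the worst post-treatment finding.

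Cover the neurological examination if it is recorded as its own field, otherwise each recorded body system. Use the number of subjects examined as the denominator and show it. For early study completers, apply the remapping of Week 24/ET to Week 8 already set in SAP 6.2.9. Say whether unscheduled examinations count towards the worst finding, since SAP 6.2.10 does not name the physical examination. Keep the listing; the Screening summary may stay as a description of the groups at entry.

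The cost is a few lines of SAP text and one more table from data already collected, with no new procedure. The drawback is low denominators for body systems skipped at shortened examinations, so the visit-level rows will be informative mainly for the neurological examination.

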6.12.7 Injection Site Evaluation

The injection site evaluation is a global evaluation of the injection site which will be assessed prior to dosing, after dosing, and on every follow up visit. Findings such as presence of erythema, edema, burning or stinging (sensation as described by the subject), itching (sensation as described by subject), bruising, and drainage will be recorded. Number of subjects that have findings related to injection site evaluation at each assessment visit will be tabulated by treatment group.

All injection site evaluation findings throughout the study will be listed.

6.12.8 C-SSRS

C-SSRS will be used to assess suicidal ideations and behaviors. Number of subjects that responded 'yes' to any of the C-SSRS Suicidal Ideation Items, as described in Section [6.2.8](#), will be presented by treatment group, and will be tabulated separately for screening and post-screening assessments. Similarly, number of subjects that responded 'yes' to any of the C-SSRS Suicidal Behavioral Items, as described in Section [6.2.8](#), will be presented by treatment group, and will be tabulated separately at screening and post-screening assessments. For subjects that were randomized under earlier versions of the protocol, that is, prior to addition of the C-SSRS on the study assessments, the screening version of the C-SSRS that were completed at the visit at which they are currently in when they signed the informed consent for the new version of the protocol (v4.0 dated 15-JUL-2019) will be not be tabulated but will be listed. Derived C-SSRS data as described in Section [6.2.8](#) will be listed for screening and post-screening assessments for all subjects.

[figure not shown]

7 INTERIM ANALYSIS

No interim analyses are planned.

8 DATA SAFETY MONITORING BOARD ANALYSIS

Data safety monitoring board (DSMB) analyses are described in DSMB analysis plan.

WORLDWIDE CLINICAL TRIALS
SCIENTIFICALLY MINDED • MEDICALLY DRIVEN

Revance Therapeutics, Inc.
1820201
Statistical Analysis Plan
Version 1.0
Issue Date 04-SEP-2020

WORLDWIDE CLINICAL TRIALS
SCIENTIFICALLY MINDED • MEDICALLY DRIVEN

Revance Therapeutics, Inc.
1820201
Statistical Analysis Plan
Version 1.0
Issue Date 04-SEP-2020

WORLDWIDE CLINICAL TRIALS
SCIENTIFICALLY MINDED • MEDICALLY DRIVEN

Revance Therapeutics, Inc.
1820201
Statistical Analysis Plan
Version 1.0
Issue Date 04-SEP-2020

WORLDWIDE CLINICAL TRIALS
SCIENTIFICALLY MINDED • MEDICALLY DRIVEN

Revance Therapeutics, Inc.
1820201
Statistical Analysis Plan
Version 1.0
Issue Date 04-SEP-2020

WORLDWIDE CLINICAL TRIALS
SCIENTIFICALLY MINDED • MEDICALLY DRIVEN

Revance Therapeutics, Inc.
1820201
Statistical Analysis Plan
Version 1.0
Issue Date 04-SEP-2020

WORLDWIDE CLINICAL TRIALS
SCIENTIFICALLY MINDED • MEDICALLY DRIVEN

Revance Therapeutics, Inc.
1820201
Statistical Analysis Plan
Version 1.0
Issue Date 04-SEP-2020

WORLDWIDE CLINICAL TRIALS
SCIENTIFICALLY MINDED • MEDICALLY DRIVEN

Revance Therapeutics, Inc.
1820201
Statistical Analysis Plan
Version 1.0
Issue Date 04-SEP-2020

WORLDWIDE CLINICAL TRIALS
SCIENTIFICALLY MINDED • MEDICALLY DRIVEN

Revance Therapeutics, Inc.
1820201
Statistical Analysis Plan
Version 1.0
Issue Date 04-SEP-2020

[figure not shown]
WORLDWIDE CLINICAL TRIALS
SCIENTIFICALLY MINDED • MEDICALLY DRIVEN

Revance Therapeutics, Inc.
1820201
Statistical Analysis Plan
Version 1.0
Issue Date 04-SEP-2020

WORLDWIDE CLINICAL TRIALS
SCIENTIFICALLY MINDED • MEDICALLY DRIVEN

[figure not shown]
Revance Therapeutics, Inc.
1820201
Statistical Analysis Plan
Version 1.0
Issue Date 04-SEP-2020

WORLDWIDE CLINICAL TRIALS
SCIENTIFICALLY MINDED • MEDICALLY DRIVEN

Revance Therapeutics, Inc.
1820201
Statistical Analysis Plan
Version 1.0
Issue Date 04-SEP-2020

WORLDWIDE CLINICAL TRIALS
SCIENTIFICALLY MINDED • MEDICALLY DRIVEN

Revance Therapeutics, Inc.
1820201
Statistical Analysis Plan
Version 1.0
Issue Date 04-SEP-2020

WORLDWIDE CLINICAL TRIALS
SCIENTIFICALLY MINDED • MEDICALLY DRIVEN

Revance Therapeutics, Inc.
1820201
Statistical Analysis Plan
Version 1.0
Issue Date 04-SEP-2020

[figure not shown]
WORLDWIDE CLINICAL TRIALS
SCIENTIFICALLY MINDED • MEDICALLY DRIVEN

Revance Therapeutics, Inc.
1820201
Statistical Analysis Plan
Version 1.0
Issue Date 04-SEP-2020

WORLDWIDE CLINICAL TRIALS
SCIENTIFICALLY MINDED • MEDICALLY DRIVEN

Revance Therapeutics, Inc.
1820201
Statistical Analysis Plan
Version 1.0
Issue Date 04-SEP-2020

[figure not shown]
WORLDWIDE CLINICAL TRIALS
SCIENTIFICALLY MINDED • MEDICALLY DRIVEN

Revance Therapeutics, Inc.
1820201
Statistical Analysis Plan
Version 1.0
Issue Date 04-SEP-2020

WORLDWIDE CLINICAL TRIALS
SCIENTIFICALLY MINDED • MEDICALLY DRIVEN

Revance Therapeutics, Inc.
1820201
Statistical Analysis Plan
Version 1.0
Issue Date 04-SEP-2020

[figure not shown]

WORLDWIDE CLINICAL TRIALS
SCIENTIFICALLY MINDED • MEDICALLY DRIVEN

Revance Therapeutics, Inc.
1820201
Statistical Analysis Plan
Version 1.0
Issue Date 04-SEP-2020

[figure not shown]
12 APPENDIX

WORLDWIDE CLINICAL TRIALS
SCIENTIFICALLY MINDED • MEDICALLY DRIVEN

[figure not shown]
Revance Therapeutics, Inc.
1820201
Statistical Analysis Plan
Version 1.0
Issue Date 04-SEP-2020

WORLDWIDE CLINICAL TRIALS
SCIENTIFICALLY MINDED • MEDICALLY DRIVEN

Revance Therapeutics, Inc.
1820201
Statistical Analysis Plan
Version 1.0
Issue Date 04-SEP-2020

WORLDWIDE CLINICAL TRIALS
SCIENTIFICALLY MINDED • MEDICALLY DRIVEN

Revance Therapeutics, Inc.
1820201
Statistical Analysis Plan
Version 1.0
Issue Date 04-SEP-2020
